Date: November 27, 2023

Title: Clinical trial in skin conditions of the foot using a cream enriched with *Melaleuca alternifolia* essential oil.

Description of document: Materials and Methods (Study Protocol: description of the clinical study, including objective and design. Statistical Analysis Plan (description of the statistical considerations for analyzing the data collected in the study) results of the study (Results obtained in the study) and Supplementary data (Annexes).

1. Material and method

Type of study, permits, and inclusion criteria

A randomized, double-blind, multicenter clinical trial was designed, developed at the facilities of the University Center of Plasencia (University of Extremadura, Spain) and at the Escola Superior de Saúde [name] (Polytechnic Institute of Castelo Branco, Portugal), from March to May 2023.

The trial was authorized by the Bioethics Committee of the University of Extremadura (Register No.: 55/2017, Annex 1) and was conducted in accordance with the ethical principles established in the Declaration of Helsinki in accordance with current legislation on biomedical research (Law 14/2007, of 3 June). In addition, all participants joined voluntarily, after signing the informed consent.

The inclusion criteria established were that the participants were free of cosmetic and pharmacological substances in their feet and nails, that they did not have any type of diagnosed allergy to the components of the cream or to the EO of choice and that they maintained correct foot hygiene. Participants who had a condition that compromised their health and had repercussions on the foot or who were under medical treatment incompatible with their participation in the trial were excluded from the study.

Sample

The initial number of participants was 65, of which 9 were excluded because they did not meet the inclusion criteria or because they did not sign the informed consent form (Figure 1). Of the remaining 56 participants, 7 were excluded due to lack of adherence, as they did not attend the review, so the final number of participants was 49 (Figure 1).

[figure not shown]

Figure 1. Flowchart according to CONSORT standards of the process of inclusion of participants in the study.

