A skin sample was taken following the standard procedure described for the diagnosis of mycosis (5). The epithelial surface was disinfected with 70° alcohol and a sample was collected from the affected area by scalpel scraping. Subsequently, the sample was analyzed using two different procedures. The 30% KOH test (35.3g/100ml distilled water) (Labbox, Barcelona, Spain) followed by conventional light microscopy observation to identify the infective fungal agent, and microbiological culture on Sabouraud dextrose agar with chloramphenicol and cycloheximide (Condalab, Torrejón de Ardoz, Madrid), at a constant temperature (between 25°C and 28°C) for 2 to 4 weeks, in order to inhibit molds and bacteria and observe the growth of the infective fungal agent. Participants with infection were considered to be those who had positive results in both tests, excluding cases in which only one test was positive.

- Bacteriological culture

A skin sample was taken following the standardized procedure for microbiological analysis (6). The skin was disinfected with 70° alcohol and a sample was taken by smear with a sterile swab from the affected surface. Again, the analysis was carried out using two distinct and independent procedures. A Gram stain was performed to identify bacteria and the sample was inoculated with Sabouraud dextrose broth (SDA) (Merck, Germany), at a constant temperature (between 27°C and 31°C) for 1 to 3 days. Participants with infection were considered to be those who had positive results in both tests, excluding cases in which only one test was positive.

Variables and statistical analysis

The following variables were analyzed: sociodemographic (sex and age), anthropometric (weight, height, and BMI), hygiene-related habits (frequency of foot washing, use of flip-flops in showers/pools, type of footwear and socks and frequency of sock change), presence or absence and type of infection, degree of hydration and concentration of EC group T0 (0%), group T1 (1%) and group T2 (0.5%). Of these variables, age, weight, height, BMI, and hydration were considered quantitative compared to the rest that were analyzed as qualitative.

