Statistical analysis was performed using the statistical analysis program IBM-SPSS Statistics for Windows version 25 (IBM Corp. Armonk, NY, USA). Some figures have been obtained using the Python programming language, using the Seaborn library (Waskom, M. L., (2021). Seaborn: statistical data visualization. *Journal of Open-Source Software*, 6(60), 3021, <https://doi.org/10.21105/joss.03021>).

Normality was assessed using the Shapiro-Wilk test. To evaluate the influence of different variables on infection remission, a Cox regression model was used, and survival curves of significant factors were plotted. To compare the efficacy of different EC concentrations, survival curves were compared using the Log-rank test. The Mann-Whitney U test was used to assess hydration averages according to sex. To check if there were improvements in hydration due to the use of the cream with different concentrations of EC (T1 and T2) compared to the control group (T0), hydration levels were compared using Kruskal-Wallis tests, using the Mann-Whitney U test with correction of p-values by the Bonferroni method for multiple comparisons.

In all statistical tests, significance was considered when p-value<0.05 and high significance when p-value<0.01.

2. Results

Analysis of the Elemental Composition of Commercial S. S.

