	East.	Err. East	IC 95%		East.	Err. East	IC 95%	
			Lim. Inf.	Lim. Sup.			Lim. Inf.	Lim. Sup.
Treatment 1%	11.61	2.68	6.36	16.86	-	-	-	-
Treatment 0.5%	14.00	4.04	6.09	21.91	-	-	-	-

Est: statistical survival test; Err. Est: statistician error; CI, confidence interval; Lim. Inf: lower bound; Lim. Sup: upper limit; "-": data not available.

Similarly, to evaluate whether the EO-enriched cream was effective against bacterial infections, the cumulative survival curves for both treatments were plotted (Figure 5). In this case, the treatment curve at 0.5% concentration showed better results than the 1% treatment curve.

[figure not shown]

Figure 5. Cumulative survival curves as a function of the two treatments for bacterial infections.

Thus, the mean time to achieve remission in the T1 group (1%) was 49.35 days, compared to 44.82 days in the T2 group (0.5%) (Table 5). This indicated that the treatment of the T2 group was better, since the infection remitted 5 days earlier on average, although when comparing both treatments using the Long-rank test, no statistically significant differences were found (p -value=0.130). Median survival was 60.00 days for treatment at 0.5%, so half of the participants in the T2 group achieved remission at the end of the study. This value could not be computed for the 1% treatment, indicating that less than half of the subjects in this group experienced resolution of the infection at the end of the trial (Table 5).

Table 5. Mean and mediansurvival time (in days) of remission of bacterial infection for the two EC concentrations.

Group	Media				Median			
	East.	Err. east.	IC 95%		East.	Err. east.	IC 95%	
			Lim. Inf.	Lim. Sup.			Lim. Inf.	Lim. Sup.
Treatment 1%	49.35	2.38	44.68	54.01	-	-	-	-
Treatment 0.5%	44.82	4.38	36.2	53.40	60.0	6.37	47.51	72.49

Est: statistical survival test; Err. Est: statistician error; CI, confidence interval; Lim. Inf: lower bound; Lim. Sup: upper limit; "-": data not available.

Relationship between infections and the rest of the variables analyzed

In relation to hygiene habits, it was found that most of the participants washed their feet daily, used flip-flops in swimming pools or showers, wore breathable footwear and cotton socks, and changed their socks daily (Table 6), although it is true that these habits did not show a statistically significant relationship with respect to the presence or absence of skin infections ($p\text{-value} \geq 0.103$) (Table 7).

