Table 6. Contingency table between hygiene habits and skin infections.

Category	Fungal infection		Total	Bacterial infection		Total
	No	Yes		No	Yes	
Frequency of foot washing						
1 time every 2 days	2 (4.88%)	-	2 (4.08%)	2 (6.90%)	-	2 (4.08%)
Daily	33 (80.49%)	8 (100.00%)	41 (83.67%)	23 (79.31%)	18 (90.00%)	41 (83.67%)
2 times a day	6 (14.63%)	-	6 (12.24%)	4 (13.79%)	2 (10.00%)	6 (12.24%)
Total	41 (83.67%)	8 (16.33%)	49	29 (59.18%)	20 (40.82%)	49
Flip flops in the shower						
No	7 (17.07%)	2 (25.00%)	9 (18.37%)	8 (27.59%)	1 (5.00%)	9 (18.37%)
Yes	34 (82.93%)	6 (75.00%)	40 (81.63%)	21 (72.41%)	19 (95.00%)	40 (81.63%)
Total	41 (83.67%)	8 (16.33%)	49	29 (59.18%)	20 (40.82%)	49
Type of footwear						
Non-breathable	18 (43.90%)	4 (50.00%)	22 (44.90%)	12 (41.38%)	10 (50.00%)	22 (44.90%)
Breathable	23 (56.10%)	4 (50.00%)	27 (55.10%)	17 (58.62%)	10 (50.00%)	27 (55.10%)
Total	41 (83.67%)	8 (16.33%)	49	29 (59.18%)	20 (40.82%)	49
Sock Type						
Cotton	21 (51.22%)	6 (75.00%)	27 (55.10%)	17 (58.62%)	10 (50.00%)	27 (55.10%)
Polyester	10 (24.39%)	-	10 (20.41%)	6 (20.69%)	4 (20.00%)	10 (20.41%)
I don't know	10 (24.39%)	2 (25.00%)	12 (24.49%)	6 (20.69%)	6 (30.00%)	12 (24.49%)
Total	41 (83.67%)	8 (16.33%)	49	29 (59.18%)	20 (40.82%)	49
Daily sock change						
1 time every 2 days	5 (12.20%)	-	5 (10.20%)	1 (3.45%)	4 (20.00%)	5 (10.20%)
Daily	32 (78.05%)	8 (100.00%)	40 (81.63%)	26 (89.66%)	14 (70.00%)	40 (81.63%)
2 times a day	4 (9.76%)	-	4 (8.16%)	2 (6.90%)	2 (10.00%)	4 (8.16%)
Total	41 (83.67%)	8 (16.33%)	49	29 (59.18%)	20 (40.82%)	49

"-": data not available, %: percentage.

Table 7. Relationship between hygiene habits and skin infections.

Variables	Fungal infection		Bacterial infection	
	χ^2	p-value	χ^2	p-value
Frequency of foot washing	1.87	0.393	1.68	0.432
Flip flops in the shower	0.00	0.976	2.66	0.103
Type of footwear	0.00	1.000	0.09	0.761
Sock Type	2.64	0.267	0.58	0.748
Daily sock change	2.15	0.542	4.08	0.252

χ^2 : Chi-Square

On the other hand, the possible relationship between anthropometric and sociodemographic variables and treatment efficacy for fungal infections was examined, where no statistically significant association was observed ($p\text{-values} \geq 0.145$) (Table 8). Therefore, for this sample, anthropometric and sociodemographic variables did not seem to be critical factors in the efficacy of treatment for fungal infections of the foot.

Table 8. Cox model for different anthropometric and sociodemographic variables and fungal infection.

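### Entry required correct foot hygiene, and so few participants washed or changed socks less than daily that these two non-significant results say little; the sock-change row of Table 7 also does not follow from Table 6

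*Combined protocol and SAP*

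**What the plan says.** Under the inclusion criteria (section 1), participants had to show "that they maintained correct foot hygiene". The term is not defined. Of 65 people, "9 were excluded because they did not meet the inclusion criteria or because they did not sign the informed consent form"; the two reasons are not counted separately.

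The variables paragraph lists the habits to be analysed: "frequency of foot washing, use of flip-flops in showers/pools, type of footwear and socks and frequency of sock change". It sets the threshold as "significance was considered when p-value<0.05" for all tests. It names no test for these cross-tabulations; Table 7 reports chi-square statistics.

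In the Results, the subsection on infections and the remaining variables concludes that "these habits did not show a statistically significant relationship with respect to the presence or absence of skin infections", with a smallest p-value of 0.103. The same sentence says that most participants washed and changed socks daily. It does not mention the entry criterion or how few people fall in the least frequent category. In Table 6 that category, "1 time every 2 days", holds 2 of 49 for washing and 5 of 49 for sock change.

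**The concern.** A test of whether infrequent washing or sock changing goes with infection needs people who do these things infrequently. Here entry is restricted on a closely related trait, and the sample contains almost none of them. A non-significant result from such a comparison does not distinguish no association from a large one. Placed beside habits that do vary, under one shared p-value bound, it reads as a negative finding of equal weight.

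The sock-change row has a second problem. Its printed statistics cannot be obtained from the counts shown, so a reader cannot verify one of the five comparisons.

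Correcting the infection counts, which disagree between Table 6 and the text, would not settle either matter: it adds no infrequent washers, and it does not explain the degrees of freedom.

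**Working it through.** **Inputs.** Table 6, written as not infected / infected.

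| Habit | Category | Fungal | Bacterial |
|---|---|---|---|
| Washing | every 2 days | 2 / 0 | 2 / 0 |
| | daily | 33 / 8 | 23 / 18 |
| | twice a day | 6 / 0 | 4 / 2 |
| Sock change | every 2 days | 5 / 0 | 1 / 4 |
| | daily | 32 / 8 | 26 / 14 |
| | twice a day | 4 / 0 | 2 / 2 |

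Totals: 8 fungal, 20 bacterial, 49 people.

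**Step 1: reproduce Table 7.** Pearson chi-square on 2 df gives washing 1.87, p=0.393 (fungal) and 1.68, p=0.432 (bacterial), as printed. Sock type reproduces, and flip-flops and footwear reproduce with the Yates correction. Only sock change does not (step 4). The smallest expected counts for washing are 2×8/49 = 0.33 and 2×20/49 = 0.82, too small for the chi-square approximation.

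**Step 2: what could washing have shown?** Compare the 2 infrequent washers with the other 47. With K infected in total, P(x infected of 2) = C(K,x)·C(49−K,2−x)/C(49,2), where C(49,2) = 1176. The two-sided Fisher p sums the probabilities no larger than the one observed.

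- Bacterial, K=20: P(0) = 406/1176 = 0.345; P(1) = 580/1176 = 0.493; P(2) = 190/1176 = 0.162. Hence p = 0.345 + 0.162 = 0.507 for x=0, 1.000 for x=1 and 0.162 for x=2. None reaches 0.05.
- Fungal, K=8: P(2) = 28/1176 = 0.024, so p = 1.000, 0.303 or 0.024. One outcome could have been significant. At assumed true rates of 40%, 60% and 80% against 17% (8/47), exact power is 12%, 26% and 47%.
- The text instead implies 28 people with any bacterial infection (19+9) and 13 with any fungal (4+9). With K=28, the smallest attainable p is 210/1176 = 0.179 (x=0). With K=13 it is 78/1176 = 0.066 (x=2).
- The observed 0 of 2 has an exact 95% upper limit of 1 − 0.025^(1/2) = 84%.

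**Step 3: sock change.** Bacterial infection was 4/5 = 80% (exact 95% CI 28 to 99%) in less-than-daily changers and 16/44 = 36% (22 to 52%) in the rest. For the five, P(4) = 0.0737, P(5) = 0.0081 and P(0) = 0.0623, so Fisher p = 0.0737 + 0.0081 + 0.0623 = 0.144. Only 5 of 5 would have been significant (p=0.008). For assumed rates of 60% or 80% against 40%, exact power is 8% or 28%. Fungal infection was 0 of 5, with upper limit 1 − 0.025^(1/5) = 52%.

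**Step 4: the sock-change row of Table 7.** From the three bacterial rows, the terms (O−E)²/E are 1.297 + 1.881 + 0.229 + 0.332 + 0.057 + 0.083 = 3.88. On (3−1)(2−1) = 2 df, p=0.144 (a coincidental match with the Fisher p in step 3). The fungal rows give 2.15, p=0.341. Table 7 prints 4.08, p=0.252 and 2.15, p=0.542. On 3 df, 4.08 gives 0.253 and 2.15 gives 0.542, so the printed p-values fit 3 df.

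A four-category variable would explain this. Splitting the bacterial row 1 / 4 into 0 / 1 and 1 / 3 gives chi-square 4.085, p=0.252 on 3 df. The fungal statistic stays at 2.15, since none of the five is fungal, and p becomes 0.542. All four printed figures are then reproduced. Against this, question 26 of the participant questionnaire offers only three answers on sock change.

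**The case against.** The strongest reply is that the entry rule has not been shown to do anything. The criterion is undefined, the nine exclusions are not split by reason, and people washing every two days were enrolled. Daily washing may simply be common. Restricting the range of an exposure costs precision and generalisability; it does not by itself bias an association. This stands. A reader might infer that the eligibility rule produced the null result, but the documents do not support that.

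Nor was the washing test decided in advance. Two fungal infections in the two infrequent washers would have given p=0.024. Table 7 also includes six twice-daily washers: with five of them and neither infrequent washer infected, the three-category bacterial chi-square would have given p=0.046; with none of them and both infrequent washers infected, p=0.027. So the claim of no attainable significance holds only for infrequent washers against the rest on bacterial infection.

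Three of the five habits do vary: footwear 22 against 27, flip-flops 9 against 40, sock type 27, 10 and 12. The argument does not reach them, although small numbers limit them too. The report also says only that no statistically significant relationship was shown; reading it as a claim that hygiene does not matter goes beyond its words.

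Finally, this is a secondary table on which efficacy does not depend, and requiring adequate hygiene in a trial of a topical product is defensible. Both are fair, and they limit the weight of the point. They do not make the two sparse comparisons informative.

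**Conclusion.** The point holds for washing and sock-change frequency only. Washing cannot be assessed usefully with 2 of 49 infrequent washers. Sock change is inconclusive: the bacterial contrast of 80% against 36% is compatible with chance, but gives no reassurance of no association. The missing caveat is that entry required correct hygiene and few participants had less-than-daily habits; cause and effect between the two is not established.

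The sock-change row of Table 7 is inconsistent with Table 6. A reader might infer that the authors merely used the wrong degrees of freedom. That is not established: a wrong df alone would not turn 3.88 into 4.08, whereas a fourth category merged in Table 6 would account for every printed figure. The documents do not settle which it is.

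These conclusions rest on Table 6's 8 fungal and 20 bacterial cases, which match neither 4 and 19 nor 13 and 28 from the text. The power figures rest on assumed infection rates, since the documents give none for planning.

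**What to change.** 1. In the Results sentence on hygiene habits, take washing and sock change out of the joint statement and say, for example: entry required correct foot hygiene, and only 2 of 49 participants washed and 5 of 49 changed socks less than daily; the sample is too sparse to assess washing frequency and is inconclusive for sock change.
2. Present those two habits as counts with exact confidence intervals.
3. Report footwear, sock type and flip-flop use in their own sentence.
4. State what correct foot hygiene meant at entry and, if the records allow, how many of the nine exclusions were for it.
5. Reconcile the sock-change categories of Tables 6 and 7: either show the fourth category or recompute from the three rows. Use an exact test either way, because the smallest expected counts in the three-row table are 4×8/49 = 0.65 (fungal) and 4×20/49 = 1.63 (bacterial).

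The cost is a few sentences, one recomputed table row and a weaker secondary conclusion. No new data are needed.

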The sample consisted of 36 women and 13 men, divided into two age groups: young people between 18 and 30 years old ($22,438 \pm 3,898$) and adults between 31 and 64 years old ($50,212 \pm 9,633$). In terms of origin, 23 were residents of Plasencia (Spain) and 26 in Castelo Branco (Portugal). The descriptive characteristics of the sample are detailed in Table 1.

Table 1. Descriptive characteristics of the sample.

VARIABLES	Total n=49	Origin	Young Men (mean±SD)	Adult Men (mean±SD)	Young Women (mean±SD)	Adult women (mean±SD)
AGE (years)	41,143± 15,485	Spain Portugal	20±2,828 26±NP	46,333±13.317 46,857±10,495	24,111±3,723 19±2	49±9,367 53.50±8.609
	70,545± 12,705	Spain Portugal	80±14,142 69±NP	87,333±17,926 80,714±11,572	68,667±13,684 66,750±8,995	64,411±7,193 66.857±11.016
HEIGHT (m)	1,664±0 ,085	Spain Portugal	1.82±0.113 1.7±NP	1.733±0.025 1.757±0.060	1,652±0.074 1.657±0.049	1.618±0.068 1,616±0.057
	25,404± 3,626	Spain Portugal	24,026±1,280 23,875±np	29,170±6,725 26,148±3,488	25,069±4,334 24,372±3,837	24,611±2,350 25,552±3,548

n: sample size; SD, standard deviation; NP: Not applicable; kg: kilogram; M: Metro; BMI, body mass index; m^2 : Square meter.

Randomization, masking, and experimental design

Participants were randomly assigned to distinct groups using free software Epidat 4.0 (2011, Galicia, Spain). The blinding was double-blind, so that neither the investigators nor the participants knew the group assigned to the participant until the completion of the study and statistical analysis.

The total number of participants was divided into three groups: a control group (T0) (n=12), in which no participants had a skin infection, and two different treatment groups (T1 and T2) (n=37), with diverse levels of EC. The rest of the participants were included in these two treatment groups, including both infected (n=32) and healthy (n=5) participants. Thus, group T1 (n=25) had 23 participants with infection and 2 healthy participants, and group T2 (n=12) had 9 participants with infection and 3 healthy participants.

The clinical evaluation of the participants was carried out before the start of treatment and, subsequently, on days 15, 30, 45 and 60 of treatment, except for cultures, both mycological and bacterial, which were performed at baseline, at 30 days and at 60 days of treatment. All reviews, sampling, and data collected were performed by the same observer.

Choice of EO, base cream, and preparation of treatments

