The determination of the specific composition of the 3 types of EO made it possible to quantify the exact concentration of the different components of each of the EO, choosing the EO with the highest concentration of components with antimicrobial activity and the lowest concentration of components susceptible to interaction with other drugs or to produce allergies in the participant, such as terpinolene, alpha-terpinene and sabinene and the aged components of EO(7-10). Specifically, the main component in the 3 EO samples was terpinen-4-ol, with a concentration between 28.47% and 29.15%, followed by gamma-terpinene and alpha-terpinene (Table 2). These three components accounted for approximately 65% of the total EO in the 3 samples analyzed. On the other hand, alpha-terpineol and eucalyptol were found to be the fourth and fifth most concentrated components, with percentages between 3.85%-5.85% and 4.12%-5.81%, respectively. These two, along with m-cymene, alpha-pinene, and terpinolene, made up about 24% of the total EO. The rest of the EO was made up of up to 22 different compounds with minority percentages, considered together as traces. For all the above results, the EO of *M. alternifolia* of the brand Esencias Lozano® was used, since it was the EO that presented the highest percentage of the components of terpinen-4-ol, eucalyptol and alpha-terpineol, whose antimicrobial activity has been described in the bibliography(7,11-14).

Table 2. Percentages of the different components according to the EO studied in the CG-MS.

Components	Trademarks of EO		
	Naissance®	Marnys®	Esencias Lozano®
Terpinen-4-ol	28.47%	29.10%	29.15%
Gamma-terpinene	21.92%	20.42%	22.86%
Alpha-Terpinene	13.10%	11.23%	13.58%
Alpha-terpineol	3.85%	4.03%	5.85%
Eucalyptol	4.12%	4.82%	5.81%
M-cymene	3.40%	5.28%	4.96%
Alpha-pinene	3.18%	3.15%	5.12%
Terpinolene	4.65%	4.26%	3.72%
Traces	17.31%	17.71%	8.95%
Total	100%	100%	100%

®: trademark; %: percentage of the component in the sample.

Test results for microbiological diagnostics

After reading the tests performed for microbiological diagnosis, it was determined that, of the 49 total participants, 32 (65.3%) were positive for skin infections. Of these 32 participants, 4 (12.5%) had fungal infection, 19 (59.4%) showed bacterial infection, and 9 (28.1%) had mixed fungal and bacterial infections simultaneously.

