Of the participants who developed skin infections, 23 were women and 9 were men. The prevalence of skin infections by sex is shown in Table 3.

Table 3. Prevalence of infections as a function of sex.

Sex	Infections			Total
	Fungal	Bacterial	Mixed	
Women	3 (9.3%)	13 (40.6%)	7 (21.8%)	23 (71.7%)
Men	1 (3.1%)	6 (18.8%)	2 (6.4%)	9 (28.3%)
Total	4 (12.4%)	19 (59.4%)	9 (28.2%)	32 (100%)

%: Percentage.

The colorations observed with Wood's light in the interdigital spaces were coral red and opaque blue (Figure 3). The coral-red coloration corresponds to a superficial bacterial infection of the skin caused by *C. minutissimum*, known as erythrasma, and the dull blue coloration corresponds to a fungal infection caused by the dermatophyte *Trichophyton schoenleinii*.

[figure not shown]

Figure 3. Fluorescence of different color emitted by pathogens under Wood's light in interdigital spaces of the feet. (A and B) erythrasma with coral-red coloration (*) and (B) suspected *Trichophyton schoenleinii* with bluish coloration (↑).

Mycological cultures were used to determine the causative agents of fungal infections. The dermatophytes and yeasts that were identified were: *Trichophyton schoenleinii*, *Trichophyton verrucosum*, *Trichophyton tonsurans* and *Candida albicans*. On the other hand, the following bacteria were identified in bacterial cultures: *Corinebacterium minutissimum*, *staphylococcus haemolyticus*, *staphylococcus epidermidis*, *staphylococcus lugdunensis*, *micrococcus luteus* and *micrococcus sp.*

Efficacy of treatments

To test whether the EC-enriched cream was effective against fungal infections, the cumulative survival curves of the two treatments, T1 and T2, were plotted (Figure 4). 100% of fungal infections resolved within 30 days with both treatments, although the EC curve at 1% was higher than 0.5%.

[figure not shown]

Figure 4. Cumulative survival curves as a function of the two treatments for fungal infections.

In fact, the mean time to achieve remission in the T1 group (1%) was 11.61 days, compared to 14.00 days in the T2 group (Table 4). However, according to the Log-rank test, the differences between the two groups were not statistically significant (p -value=0.611). Therefore, both concentrations have similar efficacy in terms of the time required to achieve remission of infection.

Table 4. Mean and median survival time (in days) of remission of fungal infection for the two EC concentrations.

Group	Media				Median			

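### The 100% fungal remission claim has no stated denominator, rests on conflicting infection counts and is at odds with Table 4, and the seven non-attenders (12.5% of 56) are not described in the text

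*Combined protocol and SAP*

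**What the plan says.** **Sample.** Sixty-five people started and 9 were removed as ineligible or not consented. Of the other 56, "7 were excluded due to lack of adherence, as they did not attend the review, so the final number of participants was 49".

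**Randomization, masking, and experimental design.** The control group T0 has 12 participants, none infected. For the others, "group T1 (n=25) had 23 participants with infection and 2 healthy participants, and group T2 (n=12) had 9 participants with infection" (the remaining 3 in T2 were healthy). Clinical evaluation took place at baseline and then "on days 15, 30, 45 and 60 of treatment, except for cultures, both mycological and bacterial, which were performed at baseline" and again at days 30 and 60.

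**Variables and statistical analysis.** Remission is analysed with survival curves, a log-rank test and Cox regression. No analysis set, event-time definition, missing-data rule or censoring rule is given.

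**Test results for microbiological diagnostics.** Of 32 infected participants, "4 (12.5%) had fungal infection, 19 (59.4%) showed bacterial infection, and 9 (28.1%) had mixed fungal and bacterial infections simultaneously". Table 3 gives the same split. By contrast, "Table 6. Contingency table between hygiene habits and skin infections" lists 8 fungal and 20 bacterial infections among the 49.

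**Efficacy of treatments.** "100% of fungal infections resolved within 30 days with both treatments", and "the mean time to achieve remission in the T1 group (1%) was 11.61 days, compared to 14.00 days in the T2 group" (Table 4; log-rank p=0.611). Table 4 has dashes for both medians. For the missing 1% median in the bacterial Table 5, the text says: "This value could not be computed for the 1% treatment, indicating that less than half of the subjects in this group experienced resolution" by the end of the trial. Tables 4, 5, 8 and 9 print no n.

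**The concern.** Two things make the absolute remission claim hard to rely on.

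First, one in eight eligible participants was set aside because they did not come back. Non-attendance can go with no benefit or irritation, or with early cure, so any bias could run either way. Survival methods can use partial follow-up, so leaving these people out was a choice, and the text gives no reason for it beyond non-attendance.

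Second, a bare 100% hides how few infections it may rest on, and the document gives two incompatible counts. The table meant to support the claim does not fit it. If the remission analysis included people without a fungal infection at baseline, they could be counted as remitted from the start and raise the apparent success.

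At stake is the absolute statement of efficacy. The comparison of the two concentrations is not shown to change.

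**Working it through.** **1. Participant flow (reproduces).** 65 − 9 = 56; 56 − 7 = 49; 7/56 = 12.5%. The printed totals rest on the 49: sex 36 + 13, site 23 + 26, groups 12 + 25 + 12, infected 32/49 = 65.3%, Table 6 41 + 8 and 29 + 20. None is 56.

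**2. Infection counts.**

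| | Diagnostic results and Table 3 | Table 6 |
|---|---|---|
| Any fungal | 4 + 9 = 13 | 8 |
| Any bacterial | 19 + 9 = 28 | 20 |

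- Eight matches none of 4, 9 or 13, and 20 matches none of 19, 9 or 28.
- Even with no overlap, Table 6 accounts for at most 8 + 20 = 28 infected participants, against 32 stated.
- Table 6 is not a simple misprint. Chi-square tests rebuilt from its counts (Yates correction for 2×2) return 8 of the 10 p-values in Table 7. Only the two for sock change differ: 0.341 against 0.542 printed, and 0.144 against 0.252 printed.

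**3. Median in Table 4.** If every infection resolved by day 30, the proportion still infected falls to 0 and must pass 50% on the way, so a median exists. Table 4 gives none for either group. Read as the text reads the same gap in Table 5, fewer than half resolved, which contradicts 100%.

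**4. Mean times in Table 4.** A survival mean is the area under the curve. If a share p is counted as remitted before day 15, and follow-up reaches day 15, the mean is at least 15 × (1 − p). Hence p ≥ 1 − mean/15.

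- T1: 1 − 11.61/15 = 22.6%
- T2: 1 − 14.00/15 = 6.7%

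The first review is at day 15 and the first follow-up culture at day 30. If times are scheduled reviews, at least about 23% of T1 and 7% of T2 records were therefore counted as remitted before any review.

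**5. Precision of 100%.** The exact (Clopper-Pearson) 95% lower limit for n out of n is 0.025^(1/n).

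- n=13: 0.025^(1/13) = 75.3%
- n=8: 0.025^(1/8) = 63.1%

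Neither n is confirmed, so these are illustrations.

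**6. Possible effect of the seven.** Assume they had the fungal prevalence of the 49 and none resolved.

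- Base 13: expected infections 7 × 13/49 = 1.86; 13/(13 + 1.86) = 87.5%
- Base 8: expected infections 7 × 8/49 = 1.14; 8/(8 + 1.14) = 87.5%

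Both reduce to 49/56, so this restates the 12.5% exclusion and does not depend on which base is right. If none of the seven had an unresolved fungal infection, the rate stays at 100%. The arithmetic extreme, all seven with an unresolved fungal infection, gives 13/20 = 65.0% or 8/15 = 53.3%; nothing in the documents makes it likely.

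**The case against.** **No printed inference is shown to change.** This stands. Bias from the seven is not demonstrated, and p=0.611 is not shown to move. If they had baseline data only, they add nothing to the survival or Cox results. Counting missing as not remitted is a conservative convention, and the text does not confirm that baseline results for the seven exist. The pooled prevalence in step 6 is also an assumption, since their group is unknown and T0 had no infections.

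**The figures are not shown.** Figure 1 may give the assignment and timing of the seven, and Figures 4 and 5 may show n, steps or censoring. The point is therefore limited to the text and tables. A reader might infer that the seven were randomised and then removed, or that they are missing from every result. The documents support neither: the text does not place the exclusion relative to assignment, and Tables 4, 5, 8 and 9 print no n from which to tell.

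**The dash in Table 4 may only mean not reported.** Its footnote defines it as data not available. But Table 5 carries the same footnote, and there the text takes the dash as fewer than half resolved. One of the two uses needs correcting.

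**Event time is undefined.** The early mean times are anomalous only if times are scheduled reviews. A reader might go further and infer that Table 4 counts more records than there were people: with times on days 0, 15 or 30 and no censoring, 11.61 = 360/31 and 14.00 = 210/15, against groups of 25 and 12. That does not follow. With whole-day times, 267/23 = 11.61 and 126/9 = 14.00, and 23 and 9 are the infected counts in T1 and T2. Whole-day times between days 1 and 30 can be constructed at those sizes that also reproduce the printed standard errors, 2.68 and 4.04. This shows only that it is possible. Those n would be all infected participants, not only those with a fungal infection.

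The 13 against 8 conflict and the missing median depend on none of these assumptions about times.

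**Conclusion.** The concern holds in this form. Seven of 56 (12.5%) were excluded for non-attendance without being described in the text, and no printed denominator is 56. The 100% fungal remission claim has no n in the text or tables, has two incompatible bases (13 and 8; bacterial 28 and 20), and conflicts with a Table 4 that lacks a median. The early mean times add to the doubt, on the condition that times are scheduled reviews. That people without a fungal infection entered the remission base is a possibility to be checked, not a finding.

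The exact lower limit is 75% or 63%, depending on the base. Under the step 6 assumptions remission ranges from 87.5% to 100%. The size and direction of any bias are unknown. What lacks support is the absolute claim, not the T1 versus T2 comparison. The correction should be made; confidence is medium because the figures are not shown.

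**What to change.** 1. Reconcile the fungal counts (13 or 8) and the bacterial counts (28 or 20).
2. For Tables 4, 5, 8 and 9, state the unit, n, events and censoring by group, and define the event time. Correct the Table 4 times and median, or the 100% claim, so that they agree.
3. Restrict each remission analysis to participants infected at baseline with that type of infection.
4. Unless Figure 1 already does so, report the seven by group, baseline infection status and last attended visit, and say whether any were never assigned.
5. Include any assigned participant with partial follow-up in the assigned group, censored at the last attended visit. Say that those with baseline data only add nothing to the survival and Cox analyses.
6. Report remission with its denominator and exact confidence interval, worded as applying to those retained.
7. Where baseline results for the seven exist, add a sensitivity analysis that counts the infected ones as not remitted.

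The cost is a small re-analysis and a few sentences, with no new data collection. Reported remission may fall. Item 7 depends on records that the text does not confirm exist.
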